1.1.3 Exploratory Objectives

To evaluate the ability of the combination ETBX-011, ETBX-051, ETBX-061 vaccine regimen to generate T-cell responses specific for Brachyury, MUC1, and CEA.

1.1.4 Primary Endpoints

- Dose-limiting toxicities (DLTs) and maximum tolerated dose (MTD) or highest tested dose (HTD).
- Treatment-emergent adverse event (AEs) and serious adverse events (SAEs).
- Clinically significant changes in safety laboratory tests, physical examinations, electrocardiograms (ECGs), and vital signs.

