2.2 SCREENING EVALUATION

All screening tests and procedures must be performed within 28 days prior to the first planned dosing of the study drug, unless otherwise noted. The following procedures and evaluations will be performed and documented in the subject's source records.

- History and physical exam including ECOG performance status and vital signs
- 12-Lead ECG
- Clinical laboratory tests (within 16 days prior to drug administration)
 - Chemistry: sodium, potassium, chloride, bicarbonate, calcium, glucose, BUN, creatinine, ALT, AST, alkaline phosphatase, total protein, albumin, and total and direct bilirubin.
 - Hematology: complete blood count (CBC) with differential and platelets
 - Coagulation panel: PT, INR, and PTT.
 - Urinalysis.
- Serum pregnancy test (β -HCG) for females of childbearing-potential and women < 12 months since the onset of menopause (within 16 days prior to enrollment)
- HBV (HBsAg), HCV (anti-HCV), HIV (anti-HIV) screening (within 3 months prior to enrollment)
- Appropriate tumor imaging and assessment. All baseline tumor measurements should be performed based on the subject's qualifying scan obtained within 28 days prior to the start of treatment.
- Confirmation of diagnosis. A report from any CAP or CLIA certified laboratory is acceptable.

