2.4 BASELINE EVALUATION

All subjects are required to complete baseline evaluations within 1 day prior to the first planned dosing of the study drug (Any screening evaluation done on D-1 of treatment can also serve for the baseline evaluation). The following procedures and evaluations will be performed and documented in the subject's source records.

- History and physical exam including ECOG performance status and vital signs
- Serum pregnancy test (β -HCG) for females of childbearing-potential and women < 12 months since the onset of menopause.
- Chemistry: sodium, potassium, chloride, bicarbonate, calcium, glucose, BUN, creatinine, ALT, AST, alkaline phosphatase, total protein, albumin, and total and direct bilirubin.
- Hematology: CBC with differential and platelets

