3.1.1 Dose Limiting Toxicity

For the purposes of dose escalation a dose limiting toxicity (DLT) is defined as:

- Any Grade 3 or greater toxicity that is possibly related to the vaccine and as defined by Common Terminology Criteria for Adverse Events (CTCAE) Version 5.0 with the exception of transient (≤ 24 hours) Grade 3 flu-like symptoms or fever, which is controlled with medical management or transient (≤ 24 hours) Grade 3 fatigue, skin reactions or rash, headache, nausea, emesis that resolves to Grade ≤ 1 or asymptomatic grade 3 amylase/lipase elevation. For purposes of dose escalation the DLT evaluation period will be for 3 weeks following the first dose of drug.

Subjects experiencing a DLT will be removed from protocol therapy.

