3.2 ADMINISTRATION AND DURATION OF TREATMENT

Each of the three ETBX vaccines will be administered on Weeks 0, 3, and 6 followed by booster vaccines every 8 weeks for up to a year. Treatment may be shorter for patients who experience progressive disease (unequivocal or confirmed) or unacceptable toxicity, withdraw consent, or if the Investigator feels it is no longer in their best interest to continue treatment. For specifics on drug administration see section [11.1.5](#).

Vital sign assessments (temperature, heart rate, blood pressure, respiratory rate) are to be obtained after the subject has been in a seated resting position for at least 5 minutes. For the first injection, vital signs must be assessed 30 and 60 minutes after the injection. Vital signs must be assessed 30 minutes after the subsequent injections.

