^e Vital signs include temperature, heart rate, blood pressure, and respiratory rate. Vital sign assessments are to be obtained after the subject has been in a seated resting position for at least 5 minutes. For the first injection, vital signs must be assessed 30 and 60 minutes after the injection. Vital signs must be assessed 30 minutes after the subsequent injections.

^f Acceptable contraceptive measures are described in Section [2.1.1.12](#).

^g Injection site reactions will be monitored

^h Subjects will be given a diary card for the self-evaluation and reporting of injection site reactions.

ⁱ All baseline tumor measurements should be performed based on the subject's qualifying scan obtained within 28 days prior to the start of treatment. Tumor imaging and assessments will be performed

^j Serum pregnancy test will be performed on females of childbearing-potential and women < 12 months since the onset of menopause. The pregnancy test will be performed at each dosing visit with the result confirmed as negative prior to dosing.

^k Serum virology test for HIV (as determined by ELISA and confirmed by western blot), and HBV and HCV (as determined by HBsAg and hepatitis C serology).

^l After the subject completes or withdraws from study therapy, the study team will contact the subject approximately every 3 months for 12 months and then approximately every 6 months for 24 months and then every 12 months thereafter for another 24 months to collect follow-up information, including survival status and any current cancer treatment regimen.

^m If the patient cannot return to the Clinical Center within 90 days after the last vaccine, the patient will be contacted by phone to AEs and laboratory assessments will be deferred until a later point if at feasible.

ⁿ See section [2.2](#) for screening criteria which are exceptions to the D-28 to D-1 screening window period.

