8 STATISTICAL METHODS

8.1 STATISTICAL HYPOTHESIS

This is a Phase I trial in subjects with advanced cancer. A combination ETBX-011, ETBX-051, ETBX-061 vaccine regimen using the same modified Adenovirus vector backbone, separately encoding three well-studied TAAs will be assessed. The vaccine will be tested at standard dose level, and a dose de-escalation (if required) design will be employed. The primary endpoint will be to determine the overall safety of combined ETBX-011/ETBX-061/ETBX-051 vaccine when administered SC to subjects with advanced solid tumors and establish a recommended phase 2 dose of vaccine. This will be reported when an MTD is determined (expected to be less than 1 year from trial start). A secondary endpoint will be to obtain preliminary data on ORR, DCR, duration of response, PFS, and OS in treated subjects (preliminary data will be assessed around two years following trial start). An exploratory hypothesis (objective) will be to evaluate the immunogenicity of the combined ETBX-011/ETBX-061/ETBX-051 vaccine.

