8.4.4 Safety Analysis

DLTs will be evaluated continuously in a dose level. An overall assessment of whether to de-escalate to the next dose level will be made at least 1 week after the last subject in the previous dose level has received their first injection. A dose level will be considered safe if $< 33\%$ of subjects treated at a dose level experience a DLT (i.e., 0 of 3, ≤ 1 of 6, ≤ 2 of 9, ≤ 3 of 10). Safety will be evaluated in 3 or 6 subjects at each dose level in the dose escalation component of the study. Safety will continue to be monitored among additional subjects treated at the MTD or HTD in the dose expansion component of the study. A subject will be considered evaluable for safety if treated with at least one injection. DLTs will be observed for 1 week.

Safety endpoints will be analyzed as summary statistics during treatment and/or as change scores from baseline assessments. AEs will be coded as defined in the Medical Dictionary for Regulatory Activities (MedDRA). All AEs will be recorded and tabulated following each treatment (vaccine injection). AEs will be recorded by severity, frequency, and relationship to the study intervention and will be presented by System Organ Class (SOC) designations and preferred term groupings. Information on each AE will include start date, stop date, severity, relationship, expectedness, outcome, and duration. Adverse events leading to premature discontinuation from the study intervention and serious treatment-emergent AEs will be presented either in a Table or a Listing.

In addition, overall safety will be assessed by descriptive analyses using tabulated frequencies of AEs by grade using CTCAE Version 5.0 within dose levels and for the overall study population in terms of treatment-emergent AEs, SAEs, and clinically significant changes in safety laboratory tests, physical examinations, ECGs, and vital signs.

The safety events listed in section [8.4.6.2](#) will trigger a temporary suspension of the study injections.:

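### ECG change is part of the primary safety endpoint, but a subject who stays on treatment has no ECG scheduled between screening and week 14, so none falls in the DLT window or at a priming visit

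*Combined protocol and SAP*

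**What the plan says.** The third primary endpoint in Section 1.1.4 is "Clinically significant changes in safety laboratory tests, physical examinations, electrocardiograms (ECGs), and vital signs". Section 8.4.4 carries it into the analysis, tabulating "clinically significant changes in safety laboratory tests, physical examinations, ECGs, and vital signs" within dose levels and overall.

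ECG collection is set in four places:

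- Section 2.2 requires a 12-lead ECG at screening, where "All screening tests and procedures must be performed within 28 days prior to the first planned dosing of the study drug", with exceptions that do not concern the ECG.
- Section 2.4 begins "All subjects are required to complete baseline evaluations within 1 day prior to the first planned dosing of the study drug" and then lists history and physical examination, pregnancy test, chemistry and hematology. It lists no ECG.
- Section 3.2 sets the checks after injection: "For the first injection, vital signs must be assessed 30 and 60 minutes after the injection". Again there is no ECG.
- The calendar in Section 3.5 marks the ECG at screening, at weeks 14, 22, 30, 38, 46 and 54, and at End of Treatment.

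On the dose decision, Section 3.1.1 says that "the DLT evaluation period will be for 3 weeks following the first dose of drug". Section 8.4.4 instead gives a 1-week DLT observation period. Section 8.1 says of the primary result: "This will be reported when an MTD is determined (expected to be less than 1 year from trial start").

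For the End of Treatment visit, footnote m of the calendar says: "If the patient cannot return to the Clinical Center within 90 days after the last vaccine, the patient will be contacted by phone". The footnote covers adverse events by phone and deferred laboratory tests. It does not mention the ECG.

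**The concern.** An endpoint can be reported only for the times at which it is measured. This combination has not been given to humans before (Section 1.2.8), and the DLT window and the three priming doses are the period on which the dose decision rests. Of the four measures in the endpoint, the ECG is the only one not scheduled in that period.

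A silent ECG change that arose after the first, second or third dose and resolved before week 14 would not be found by following the calendar. A report of no clinically significant ECG change would then partly reflect when ECGs were taken. Because the primary result is reported once the MTD is determined, that statement could be made with little or no scheduled post-dose ECG data behind it.

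**Working it through.** The plan gives no figure to reproduce. The check is to align the calendar rows and then count days.

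**Step 1: align the rows.** The ECG row has 12 cells, matching the 12 columns of the calendar in Section 3.5.

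| Measure | Screening | Wk 0 | Wk 3 | Wk 6 | Wks 14–54 (six visits) | End of Treatment | Follow-up |
|---|---|---|---|---|---|---|---|
| 12-lead ECG | X | – | – | – | X at all six | X | – |
| Physical examination | X | X | X | X | X at all six | X | – |
| Vital signs | X | X | X | X | X at all six | X | – |
| Chemistry, CBC | X | X | X | X | X at all six | X | – |

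The blanks are not a table-reading fault: the other rows align to the same columns, and Section 2.4 independently leaves out the ECG. A subject who completes treatment has 1 ECG before dosing and 6 + 1 = 7 after it. Of those 7, 0 are at weeks 0, 3 or 6.

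**Step 2: gaps for a subject who continues.** Day 0 is the first dose. Dose 3 is at week 6 = day 42. Visits may move by 1 week (Section 3.3).

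- First on-treatment ECG: 14 × 7 = day 98, or day 91 at the early edge of the window.
- After a 3-week DLT window: 98 − 21 = 77 days (early edge 91 − 21 = 70).
- After a 1-week DLT window: 98 − 7 = 91 days (early edge 91 − 7 = 84).
- After dose 3: 98 − 42 = 56 days.
- From the screening ECG, taken 1 to 28 days before dosing: 98 + 1 = 99 to 98 + 28 = 126 days.

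**Step 3: timing of the dose decision.** Section 3.1.2 requires at least 3 days between successive subjects. At the fastest accrual the sixth subject starts on day 5 × 3 = 15.

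- 3-week window: decision from day 15 + 21 = 36.
- 1-week window: decision from day 15 + 7 = 22.

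Both precede the first subject's week-14 ECG on day 98. Slower accrual can change this. If the sixth subject starts more than 98 − 21 = 77 days after the first (3-week window), or more than 98 − 7 = 91 days (1-week window), the first subject's week-14 ECG exists by the time of the decision. It still lies outside that subject's own DLT window.

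**Step 4: subjects who stop before week 14.** Their only scheduled post-dose ECG is at End of Treatment, due at any time up to 90 days from the final vaccination (Sections 3.5 and 3.7). Its latest nominal day is:

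- stopped after dose 1: 0 + 90 = 90
- stopped after dose 2: 21 + 90 = 111
- stopped after dose 3: 42 + 90 = 132

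It can be much earlier, and so can precede week 14, but it follows the decision to stop. If a phone contact replaces the visit, there may be no post-dose ECG.

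**The case against.** The strongest reply is that the endpoint can be assessed as planned. Section 1.1.4 sets no timing for the ECG, the calendar supplies ECGs before and after dosing, Section 2.1.2 excludes clinically significant heart disease, and the adverse event tables for ETBX-011 alone in Section 11.1.2 list no cardiac diagnosis. This lowers the expected risk. It does not explain why one of four measures in the same endpoint is absent from the period that matters most, and the ETBX-011 experience is with one vaccine, not three together.

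Other parts of the reply stand, and they rule out stronger readings that a reader might infer:

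- *ECGs cannot inform the DLT decision at all.* Not supported. With listed exceptions, Section 3.1.1 counts any possibly related toxicity of Grade 3 or greater, however it is found. A symptomatic event, or an ECG done for clinical reasons, could count. Adverse events, physical examination and vital signs are collected at weeks 0, 3 and 6.
- *The priming course has no ECG follow-up.* Not supported. The week-14 ECG comes after all three priming doses and can show lasting change. Early leavers have the End of Treatment ECG unless that visit is replaced.
- *Few subjects will reach the booster visits.* The documents give no retention forecast. The nearest figure, 3 stable-disease events among 32 subjects (Section 1.2.6.3), is not a discontinuation rate. It comes from heavily pretreated metastatic colorectal cancer in a three-dose trial, whereas this trial also admits resected disease (Section 2.1.1).

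**Conclusion.** The point holds for protocol-scheduled ECGs. For subjects who stay on treatment, none falls in the DLT window under either stated length, and none at weeks 0, 3 or 6. The first is at about day 98. The shortfall is in systematic detection of silent or transient change during priming; symptomatic and lasting changes can still be found.

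This rests on the calendar as printed and on nominal visit days. It needs no attrition rate: with every subject retained, the count at priming visits is still 0 of 7. How much ECG data the primary report would hold depends on accrual speed. At the fastest permitted accrual, no subject has reached week 14 when the dose decision can be made. Nothing in the documents points to an actual cardiac signal. This should be corrected, because the plan as written leaves part of a primary endpoint unmeasured in the period that decides the dose, and the correction is cheap.

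**What to change.** Reconcile Sections 1.1.4 and 8.4.4 with Sections 2.4 and 3.5:

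1. Mark the 12-lead ECG at the existing week 3 and week 6 visits, and state whether it precedes the injection.
2. Optionally drop two late-booster ECGs, for example weeks 38 and 46.
3. In Section 8.4.4, report ECG findings by time since dose, with the number of subjects who have an ECG at each time.
4. Reconcile the 3-week DLT period in Section 3.1.1 with the 1-week period in Section 8.4.4. With the 1-week visit window, the week 3 visit spans days 14 to 28, so its ECG may fall outside a 21-day period and will fall outside a 7-day one. How ECG data enter the dose decision is for the sponsor to settle once those sections agree.

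If ECGs are not added, the report should state that the ECG component does not cover the DLT and priming period.

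Cost: one calendar row and no new visits. If two late ECGs are dropped, a subject who completes treatment still has 8 in all (8 + 2 − 2), with fewer late ones. A subject who leaves before the late boosters has up to two more than now, so the trial total is not necessarily unchanged. One limit remains: an ECG about three weeks after a dose will miss a change that resolves within days.

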1.1.5 Secondary Endpoints

- Objective response rate (ORR; confirmed complete or partial response) according to the Response Evaluation Criteria in Solid Tumors (RECIST) Version 1.1.
- Disease control rate (DCR; confirmed response or stable disease [SD] lasting for at least 6 months).
- Duration of response.
- PFS
- OS

1.1.6 Exploratory Endpoints

- Immunogenicity via the induction of antigen-specific T cells of the combination ETBX-011, ETBX-051, ETBX-061 vaccine regimen by flow cytometric analysis, and analysis in sera of sCD27 and sCD40L.

1.2 BACKGROUND AND RATIONAL

1.2.1 Overall Objective

As a result of the discovery of new biomarkers associated with tumor development and metastasis, many tumor-associated antigens (TAAs) are being utilized in immunotherapeutic modalities designed to induce anti-tumor directed cytotoxic immune responses. It is increasingly clear that not any one of these TAA is sufficient, as a single entity, by which one can develop a potent immunotherapeutic response. Furthermore, the addition of immune checkpoint inhibitors has augmented the immunotherapy approach against TAAs. Consequently, our efforts are focused on developing multi-targeted approaches. The overall goal of the current project is to expand our immunotherapeutic approach for the treatment of advanced cancer employing a multi-targeted approach. Safety and ability to generate CEA-specific T-cell responses in metastatic colorectal cancer (mCRC) patients using our Ad5 [E1-, E2b-]-CEA(6D) (ETBX-011) immunotherapeutic as a single agent has been achieved in a clinical setting(1, 2). Patients in that study exhibited evidence of a favorable survival probability, with all 25 patients treated at least 2 times with vaccine exhibiting a 12-month overall survival probability of 48%, with a mean overall survival of 11 months. The phenotypic heterogeneity in terms of expression of different TAAs in a given primary or metastatic tumor mass is a well-established phenomenon(3-7). One can speculate that the use of an immunotherapeutic vaccine regimen targeting three distinct TAAs, each of which is widely expressed on the majority of human carcinomas, would be potentially therapeutically advantageous over the use of a vaccine targeting only one TAA. With the safety and immunogenicity of Ad5 [E1-, E2b-]-CEA established in patients as a single agent, a multi-target approach is now being investigated. The objective is to develop a combination immunotherapeutic approach designed to induce broad anti-tumor immune responses directed against tumors that over express CEA, MUC1, and/or Brachyury. Preclinical studies were recently published indicating that this multi-targeted CEA, MUC1, Brachyury Ad5 combination vaccine induces immune responses directed against all three target CEA, MUC1, and Brachyury antigens with minimal to no “antigenic competition” in human *in vitro* studies or in murine vaccination studies(8). Testing of a combination multi-targeted CEA, MUC1, and Brachyury targeted adenoviral vector-based vaccines in a phase 1 clinical trial is planned to test the safety, ability to generate T-cell responses to each tumor antigen, and efficacy of the immunotherapeutic. Subsequent trials will involve the use of this vaccine in combination with checkpoint inhibitor monoclonal antibodies (MAbs) and other immune modulators.

1.2.2 Brachyury Expression in Cancer and Its Use as an Immunotherapy Target

Brachyury is an embryonic transcription factor of the T-box family that regulates the formation of the posterior mesoderm in the developing embryo, a process that requires the conversion of epithelial cell layers into mesenchymal cells(9). While in the majority of adult normal tissues Brachyury is undetectable, with the exception of low levels found in normal testis, thyroid and a subset of B cells (10, 11), aberrantly high levels of Brachyury have been observed in the primary and/or metastatic sites of non-small cell (NSCLC) and small cell (SCLC) lung cancer (12, 13), colon (14), hepatocellular (15), prostate (16) and breast carcinomas (17), including triple negative breast cancer (TNBC) (18). High levels of Brachyury are also characteristic of the rare tumor type chordoma (19, 20), which is thought to originate from remnants of the embryonic notochord where Brachyury is normally found. Recent studies have now characterized the role of

Brachyury in the biology of carcinomas and demonstrated the ability of this transcription factor to drive the phenotypic conversion of tumor cells from an epithelial to a mesenchymal-like phenotype (also designated as an epithelial-mesenchymal transition, EMT, or carcinoma “mesenchymalization”) (21, 22). Carcinoma cells undergoing this phenotypic transition exhibit enhanced motility and invasiveness *in vitro*, propensity to metastasize *in vivo*, and features of tumor stemness (23), including resistance to a range of therapeutics such as chemotherapy, radiation, small molecule therapies and, potentially, immunotherapy (24-27). In agreement with a role for Brachyury in the progression of carcinomas, multiple studies have now shown that the level of Brachyury in the primary tumor correlates with poor patient prognosis in carcinomas of the lung (28), colon (14), breast (17), triple negative breast (18) and gastrointestinal stromal tumor (GIST) (29). Brachyury expression has also been shown to be correlated with advanced stage prostate cancer (16).

Transcription factors have been considered “difficult to drug” due to their primary location in the nucleus and lack of a hydrophobic groove for drug attachment. Studies have shown, however, that Brachyury-specific T cells can be generated both *in vitro* and *in vivo* (30, 31). Utilizing 9-mer peptides of the Brachyury protein, for example, Brachyury-specific CD8⁺ T cells have been expanded *in vitro* from the blood of cancer patients; these Brachyury-specific CD8⁺ T cells were utilized in cytotoxic assays for effective lysis of human tumor cells that endogenously express Brachyury (30, 31).

The inherent immunogenicity of Brachyury was also revealed from the analysis of immune responses in cancer patients immunized against CEA or PSA. In addition to generating responses against the tumor-associated antigens contained within their respective vaccines, development of Brachyury-reactive CD8⁺ T cells was also observed(32). This expansion of Brachyury-specific T cells may have been the result of cross-presentation of the antigen to the immune system, following tumor destruction in response to the vaccine. These studies demonstrated that Brachyury is immunogenic, and has the potential to function as a target for anticancer vaccination. In addition, two recently completed Phase I clinical studies with a recombinant yeast-Brachyury vaccine(33) or an MVA-Brachyury-TRICOM vaccine(33, 34) also demonstrated the generation of Brachyury-specific T cells as well as safety in humans, thus providing further evidence of immunogenicity(35). These combined properties, i.e., tumor-restricted expression, relevant function in tumor progression, and immunogenicity, make Brachyury a potential target for immunotherapy-mediated approaches against cancer. Preventing or reverting the EMT process in carcinomas via the use of Brachyury-based cancer vaccines represents an attractive modality to minimize tumor dissemination and the emergence of therapeutic resistance.

